#### 6.1.4 Other study parameters

- Body weight (kilograms)
- Height (centimetres)
- Blood pressure and heart frequency
- Body temperature (axillary)
- Upper arm circumference
- Date of birth
- Place of birth
- Place of residence
- Gender (male/female)
- Sexual orientation
- Nationality
- Level of education (none, primary school, secondary school, vocational, higher education, unknown)
- Occupational history
- Civil state (single, married, widowed, separated, divorced, unknown)
- Ethnicity
  - If indigenous: specific indigenous ethnicity
- Dental state (good / plaque / inflamed gums / broken or missing teeth)
- Symptoms (including onset and intensity)
  - Cough
  - Sputum or haemoptysis
  - Weight loss

- Night sweats
- Chest pain
- Dyspnea
- Other
- Medical history and co-morbidities
- Previous diagnosis/treatment for TB (year and duration of treatment in months)
- Location in prison (cell, hallway, yard, others)
- Date of current prison entry, previous prison entries
- Medication (especially antibiotics)
- Smoking
- Drug use
- Factors influencing breath signal: intake and timing of ingestion of food, drinks, cigarettes
- CAD4TB® output score
- Radiological severity of TB
- AeoNose™ breath profiles
- GeneXpert® cycle time (if positive)
- MGIT™ culture time-to-positivity (if positive)
- Clinical severity of TB (TBscore, Wejse et al. 2008 and TBscorell, Rudolf 2014)
- CXR abnormalities as described by study doctor (infiltrate, cavity, lymphadenopathy, mass lesion, pleural abnormality, etc.)

## 6.2 Study procedures

AeoNose™:

Participants will be asked to produce a breath sample by tidal breathing through the AeoNose™ device for 5 minutes. In case of interruption (e.g. cough) the interval between stop and re-start will be recorded. Participants will use a nose clamp to avoid inhaling unfiltered air. The air sample collection will be performed under standardized conditions in a room free of gases with no small molecules (such as alcohol) that can influence the breath profile of the participant. The exhaled-breath signals will be stored on the study computer and later sent to The eNose Company for analysis.

## Digital CXR and CAD4TB®:

X-ray image will be taken using a digital X-ray system connected with CAD4TB® software. Participants will be asked to stand in front of the panel while one posterioranterior X-ray image is taken. Images will be processed by the CAD4TB® software. A TB likelihood output score is presented to the doctor within minutes. Study doctors will also view and interprete the digital CXR during the consultation.

## Sputum induction:

Participants with presumptive TB will be asked to produce two sputum samples. If necessary sputum can be induced using saline nebulisation sputum. The technique of sputum induction consists of inhaling an aerosol of saline over period of two minutes. This procedure will be preferably carried out in open air using a portable nebulizer and saline solution provided by the researchers. Participants are then instructed to expectorate in a standard sputum container.

## 6.3 Collection of data

Data collected during the screening will be recorded using electronic CRF's on the Castor EDC (electronic data capture) platform. (Castor EDC, Amsterdam, the Netherlands) Data will be inserted immediately and stored securely in the Castor study database. Information will be linked to a unique study ID number and contain no personal identifying information.

AeoNose™ breath profiles data, CXR images and CAD4TB® output will be securely stored and linked to the participant ID number.

After the breath profiles have been shared with The eNose Company they will be stored indefinitely (anonymized and encrypted) on a server in Amsterdam, the Netherlands.

## 6.4 Withdrawal of individual participants

Participants can leave the study at any time for any reason if they wish to do so without any consequences. All participants included for follow-up will be educated about their presumptive diagnosis and encouraged to follow-up either inside or outside the prison. The investigator can decide to withdraw a participant from the study for medical reasons (e.g. hospitalization for a non-TB illness).

6.5 Replacement of individual participants after withdrawal or lost to follow-up Not applicable

#### 6.6 Follow-up of participants withdrawn from treatment

Not applicable

## 6.7 Premature termination of the study

Potential reason for (a temporarily interruption or) premature ending of the study are if the security of participants and researchers or quality of the study can not be guaranteed in the Paraguayan prison environment. In case the study is ended prematurely, the sponsor will notify the accredited MREC within 15 days, including the reasons for the premature termination.

## 7. SAFETY REPORTING

## 7.1 Temporary halt for reasons of participant safety

In accordance to section 10, subsection 4, of Dutch Medical Research Involving Human Participants Act (WMO), the sponsor will suspend the study if there is sufficient ground that continuation of the study will jeopardise either the study team or participants health or safety. The sponsor will notify the accredited MREC (Laboratorio Central de Salud Publica, LCSP, Asunción, Paraguay) without undue delay of a temporary halt including the reason for such an action. The study will be suspended pending a further positive decision by the accredited MREC. The investigator will take care that study participants are kept informed.

In this study the safety risk is primarily the potential for aggressive or violent behaviour by PPL against other PPL, employees or members of the study team. The prison officials will ensure the safety of the study team and participants during the study.

## 7.2 AEs, SAEs and SUSARs

## 7.2.1 Adverse events (AEs)

Adverse events are defined as an undesirable or harmful experience occurring to a participant during the study. All adverse events, whether or not considered related to study procedure, which are reported spontaneously by the participant or observed by the investigator or his staff will be recorded. Potential adverse events are not expected in this study.

## 7.2.2 Serious adverse events (SAEs)

There is no risk of (serious) adverse events involved in participation in this study.

#### 7.2.3 Follow-up of adverse events

Not applicable

## 7.2.4 Data Safety Monitoring Board / Safety Committee

Because the study investigations do not carry a health risk for the participants no Data Safety Monitoring Board will be installed.

## 8. STATISTICAL ANALYSIS

All data will be analysed using SPSS software. (IBM, United States) The data of the participants will be analysed cross-sectional. Follow-up of participants with presumptive TB but negative microbiological testing will be completed until 6 months after Visit 1. After a

follow up period of 6 months a final diagnosis will be made (either healthy or TB case and the participant will be offered treatment if indicated). A p-value (two-sided) < 0.05 is considered to indicate a statistically significant difference in all comparisons. Multivariate analysis will be performed to analyse influences of different combinations of participant characteristics.

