#### SUMMARY

Rationale: Despite being a curable disease, each day thousands of people die of tuberculosis (TB) worldwide. TB diagnosis is often delayed, increasing the likelihood of transmission. The aim of the World Health Organization (WHO) "End TB Strategy" is to end the global pandemic by 2035. To be able to succeed, better point-of-care (POC) tests are urgently needed to improve screening of high-risk populations. Prisons are recognized worldwide as high risk environments for the concentration, amplification and transmission of TB among prisoners and their communities outside. Paraguayan penal institutions are known to have very high incidence rates of active TB (3000-5000/100.000, according to Paraguayan Ministry of Justice). Two diagnostic tools for TB screening in high risk groups need additional validation: the AeoNose™, an 'electronic nose device' for breath sampling, and digital chest X-ray (CXR) with computer aided detection with CAD4TB® software. This study will systematically screen prisoners and its' employees for TB, test the diagnostic performance of AeoNose™ and CAD4TB® and assess prison *Mycobacterium tuberculosis* epidemiology through several objectives: **Objective**: 1. Assessment of the sensitivity and specificity of the AeoNose™ and its utility for mass TB screening in high incidence settings. 2. Evaluation of the feasibility and utility of CAD4TB® digital CXR as a mass screening tool for TB. 3. Identification of factors that affect diagnostic accuracy of AeoNose™ and CAD4TB®. 4. Assessment of TB epidemiology in Paraguayan prisons and identification of mycobacterial strains. 5. Assessment of cost effectiveness of different screening algorithms. 6. Characterization of transmission dynamics and potential measures for transmission reduction. Study design: Diagnostic cohort study. Study population: Detainees (PPL) of Paraguayan penal institutions as well as their employees. Main study parameters/endpoints: 1. Number of TB cases diagnosed with GeneXpert® and/ or culture of Mycobacterium tuberculosis complex. 2. Number of TB cases correctly identified by AeoNose™. 3. Number of TB cases correctly identified by CAD4TB®. 4. Costs and effectiveness of different screening algorithms. 5. Mycobacterium tuberculosis complex

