## 6.1.2 Main study parameter/endpoint

- 1. The total number of TB cases found by GeneXpert® and/ or culture of Mycobacterium tuberculosis complex.
- 2. Number of TB cases correctly identified by AeoNose™.
- 3. Number of TB cases correctly identified by digital X-ray with CAD4TB®.
- Factors affecting or influencing sensitivity and specificity of AeoNose™ and CAD4TB®, e.g. medication use, smoking and drugs, co-morbidities, BMI, dental status

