#### 6.1.3 Secondary study parameters/endpoints

- Costs of different (theoretical) screening algorithms using AeoNose™, CAD4TB® or both in conjunction.
- 2. Signal differences and diagnostic performance of AeoNose™ and CAD4TB® in:
  - a. HIV cases (and CD4 count if available)
  - b. Patients with syphilis (and disease stage if available)
  - c. Diabetes cases (insulin dependent or non-insulin dependent)
  - d. Cases of EPTB
- 3. Number of incidental CXR findings and the effect on CAD4TB® output score.
- 4. Numbers of Mycobacterium tuberculosis complex bacterial strains identified.

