#### 8.1 Primary study parameter(s)

Primary study parameters are the number of TB cases cases by CAD4TB® CXR analysis and AeoNose™ breath sampling.

A binary assessment of the presence or absence of illness has four possible outcomes: true positives (TP), false positives (FP), true negatives (TN) and false negatives (FN). The relationship of the four outcomes is the basis of sensitivity and specificity analysis which determines the accuracy and predictive value of a diagnostic tool.

*True positive:* A positive test result in a confirmed TB case.

*False positive*: A positive test result with negative sputum results and no confirmed TB during follow-up.

*True negative*: A negative test result with no confirmed TB during follow-up. *False negative*: A negative test result with confirmed TB during follow-up.

Receiver operating characteristics (ROC) will be generated using an ROC package, and bootstrapping to generate confidence intervals in the ROC plot. T-testing or McNemar's test will be used to compute P values when comparing the sensitivity of conventional screening and CAD4TB® and AeoNose™ at assumed levels of specificity. We will also use multivariate analysis to analyse influences of different combinations of participant characteristics.

CAD4TB®: The collection of digital CXR images will be analysed and compared to presumptive and confirmed cases. The number of true/false positives and negatives will be used to calculate sensitivity and specificity as described above. The predictive value of the test will be analysed.

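### Main endpoints differ between the Summary, 6.1.2 and 8.1; separately, the unadjusted 0.05 rule gives the search for accuracy factors a false-positive risk far above 5%

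*Protocol*

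**What the plan says.** **Endpoints.** The Summary gives five main endpoints: TB cases by the reference tests, cases identified by AeoNose, cases identified by CAD4TB, "Costs and effectiveness of different screening algorithms", and strains found by sequencing. Section 6.1.2 gives four: the first three of these, plus factors affecting the accuracy of either device, "e.g. medication use, smoking and drugs, co-morbidities, BMI, dental status". Section 6.1.3 lists as secondary both "Costs of different (theoretical) screening algorithms using AeoNose" (CAD4TB, or the two together) and "Numbers of Mycobacterium tuberculosis complex bacterial strains identified". Section 8.1 begins "Primary study parameters are the number of TB cases cases by CAD4TB" and adds only AeoNose. Section 2 has three primary objectives, with no ranking; the third is to identify factors that affect the accuracy of both devices.

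**Significance rule.** Section 8 says: "A p-value (two-sided) < 0.05 is considered to indicate a statistically significant difference in all comparisons". It also plans multivariate analysis of various combinations of participant characteristics. Section 8.1 repeats that plan and adds P values for comparing the sensitivity of conventional screening, CAD4TB and AeoNose at assumed specificity levels, whose number is not given. The protocol states no hierarchy, alpha split or adjustment.

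**The concern.** There are two separate problems.

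First, costs and strains are main in one place and secondary in another, and factors are main in 6.1.2 but missing from the Summary's endpoints. An analysis plan written from this protocol would have to choose between the lists, and so would a report.

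Second, identifying factors is a primary objective, yet the stated criterion is an unadjusted 0.05 for every comparison over an open list of factors and unspecified combinations. Under that rule a factor can be declared to affect a device's accuracy when none does. The finding could then shape who is thought suitable for breath or CXR screening.

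**Working it through.** **Step 1: the lists side by side**

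| Item | Summary | 6.1.2 | 6.1.3 | 8.1 |
|---|---|---|---|---|
| TB cases by reference tests | main | main | – | not named |
| AeoNose result | main | main | – | primary |
| CAD4TB result | main | main | – | primary |
| Factors affecting accuracy | absent | main | – | not a named parameter; multivariate analysis mentioned |
| Costs | main | – | secondary | – |
| Strains | main | – | secondary | – |

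Only the two device results have the same status wherever main endpoints are listed.

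**Step 2: the plan's own figures**

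The sample size in section 3 rests on expected cases: 5000 × 0.03 = 150 and 5000 × 0.05 = 250. This reproduces the stated 150–250. It is a case count, not a power calculation, so no planned comparison has a stated power. The only error rate given is 0.05 per comparison.

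**Step 3: chance of at least one false positive**

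Inputs from the protocol: 0.05 per test (section 8), two devices, and five named factor groups (6.1.2). Assumed: the number of tests m, and that no factor has an effect.

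For independent tests the chance is 1 − 0.95^m, and the expected number of false positives is 0.05 × m.

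- 5 factors × 2 devices: m = 10; 1 − 0.95^10 = 0.401; 0.5 expected.
- 5 factors × 2 devices × (sensitivity, specificity): m = 20; 1 − 0.95^20 = 0.642; 1.0 expected.
- Smoking and drugs counted separately, 6 × 2 × 2: m = 24; 1 − 0.95^24 = 0.708; 1.2 expected.
- Three pairwise sensitivity comparisons at one specificity: m = 3; 1 − 0.95^3 = 0.143.

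The four secondary subgroups in 6.1.3 add to this. HIV, syphilis and diabetes give 3 × 2 × 2 = 12 tests. The extrapulmonary group contains only cases, so it has no specificity and gives 1 × 2 = 2. The total is 20 + 14 = 34 tests, and 1 − 0.95^34 = 0.825. If the three pairwise comparisons were made at two specificity levels (an assumption), the total is 34 + 6 = 40, and 1 − 0.95^40 = 0.871.

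**Step 4: correlated tests**

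A simulation of equally correlated two-sided z-tests (100,000 runs) gave:

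| Tests | Correlation 0.3 | Correlation 0.5 |
|---|---|---|
| 10 | 35% | 29% |
| 20 | 54% | 42% |
| 24 | 59% | 46% |

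**Step 5: share of declared factors that would be false**

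This is a different quantity: (1 − π) × 0.05 / [(1 − π) × 0.05 + π × power], where π is the share of tested factors that are real. Both inputs are assumed.

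- π = 0.10, power 0.30: 0.045 / (0.045 + 0.030) = 60%.
- π = 0.25, power 0.50: 0.0375 / (0.0375 + 0.125) = 23%.
- π = 0.50, power 0.80: 0.025 / (0.025 + 0.40) = 6%.

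**The case against.** The strongest reply has five parts.

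- **The main accuracy results are estimates.** AeoNose accuracy has Wilson intervals, ROC plots have bootstrap intervals, and the sample size rests on case counts. This stands: multiplicity touches the factor tests and the pairwise comparisons, not the sensitivity and specificity estimates.
- **The endpoint conflict does not feed the multiplicity.** A reader might infer that every listed endpoint is tested at 0.05. The protocol attaches no test to the case count, costs or strains, so the two problems must be kept apart. That also stands.
- **The lists overlap more than their lengths suggest.** Both devices appear in all three, and 8.1 mentions multivariate analysis under its primary heading. The Summary may simply have merged the primary and secondary items that section 2 separates. This explains the discrepancy without removing it: costs and strains still have two statuses, and factors are still absent from the Summary's endpoints.
- **Adjustment and factor lists are commonly left to an analysis plan,** which is not at hand. That would answer a complaint about silence. Here the protocol states a rule for all comparisons and makes factor identification a primary objective.
- **The percentages depend on assumed test counts and independence.** True, and the lower figures in the working reflect it. Even 10 tests at correlation 0.5 give 29%, well above 5%.

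**Conclusion.** The concern holds as two limited points: the main endpoints are listed inconsistently, and the stated 0.05 rule makes at least one spurious factor likely, or at least far more probable than 5%, when no factor matters. For the five named factors on two devices the chance is 40% (10 independent tests), 64% (20 independent tests) or about 42–54% (20 correlated tests). Test counts and correlations are assumptions, because the protocol fixes neither.

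Three stronger readings are tempting but not supported.

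- **That most identified factors would be chance findings.** One expected false positive in 20 tests does not show this. The false share runs from 6% to 60%, depending on inputs the protocol does not give.
- **That any favourable comparison could be presented as primary.** No list names a pairwise comparison, clinical subgroup or combination of characteristics as a main endpoint; only factors have that status, in 6.1.2.
- **That the study needs one primary result.** Two index tests can be co-primary in a diagnostic accuracy study. Ranking one above the other would be a preference.

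The study is not invalidated. What suffers is the interpretation of one primary objective and of the pairwise comparisons.

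**What to change.** 1. Use the same list in the Summary, 6.1.2 and 8.1: AeoNose accuracy and CAD4TB accuracy as primary (co-primary is acceptable), with costs and strains secondary as 6.1.3 already has them. Give factors one stated status in all three places.
2. Replace the sentence in section 8 that applies 0.05 to every comparison. Report factor, combination and subgroup results as estimates with 95% confidence intervals, labelled exploratory, or use false-discovery control if significance is to be declared.
3. Apply Holm to the three pairwise sensitivity comparisons at one specificity fixed in advance: the smallest P value against 0.05 / 3 = 0.0167, the next against 0.05 / 2 = 0.025, the last against 0.05, stopping at the first that fails.

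The cost is wording in the Summary, 6.1.2 and section 8, and slightly less power for the pairwise tests. No extra participants or data are needed.

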#### 8.1 Primary study parameter(s)

Primary study parameters are the number of TB cases cases by CAD4TB® CXR analysis and AeoNose™ breath sampling.

A binary assessment of the presence or absence of illness has four possible outcomes: true positives (TP), false positives (FP), true negatives (TN) and false negatives (FN). The relationship of the four outcomes is the basis of sensitivity and specificity analysis which determines the accuracy and predictive value of a diagnostic tool.

*True positive:* A positive test result in a confirmed TB case.

*False positive*: A positive test result with negative sputum results and no confirmed TB during follow-up.

*True negative*: A negative test result with no confirmed TB during follow-up. *False negative*: A negative test result with confirmed TB during follow-up.

Receiver operating characteristics (ROC) will be generated using an ROC package, and bootstrapping to generate confidence intervals in the ROC plot. T-testing or McNemar's test will be used to compute P values when comparing the sensitivity of conventional screening and CAD4TB® and AeoNose™ at assumed levels of specificity. We will also use multivariate analysis to analyse influences of different combinations of participant characteristics.

CAD4TB®: The collection of digital CXR images will be analysed and compared to presumptive and confirmed cases. The number of true/false positives and negatives will be used to calculate sensitivity and specificity as described above. The predictive value of the test will be analysed.

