#### Follow-up of presumptive TB cases

Participants who are considered presumptive cases of TB at Visit 1, but with negative sputum results or unable to produce sputum, will be followed-up after three and six months.

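### Section 8.1 counts as false negatives only TB confirmed during follow-up, so a device miss confirmed on Visit 1 sputum is scored, read literally, as a true negative, and sensitivity and NPV are overstated

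*Protocol*

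**What the plan says.** Section 8.1 gives the four cells from which sensitivity and specificity are to be computed:

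- True positive: "A positive test result in a confirmed TB case". No time limit.
- False positive: "A positive test result with negative sputum results and no confirmed TB during follow-up". Sputum and follow-up are two separate conditions.
- True negative: "A negative test result with no confirmed TB during follow-up". Sputum is not mentioned.
- False negative: "A negative test result with confirmed TB during follow-up". Sputum is not mentioned.

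Section 3 separates one primary visit from two follow-up visits at three and six months. Under its heading on follow-up of presumptive cases, it gives those visits to participants who were presumptive at Visit 1 "but with negative sputum results or unable to produce sputum, will be followed-up after three and six months". Section 8 repeats the restriction: "Follow-up of participants with presumptive TB but negative microbiological testing will be completed until 6 months after Visit 1".

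Section 6.1.1 defines a bacteriologically confirmed case by GeneXpert or culture, whenever obtained. The first main endpoint in section 6.1.2 is "The total number of TB cases found by GeneXpert" and/or culture, again without a time limit.

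**The concern.** The disease side of the two-by-two table is defined differently according to the index-test result. A test-positive participant is a case if TB is confirmed at any time. A test-negative participant is a case only if TB is confirmed in a phase that people with positive Visit 1 sputum never enter.

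Such participants can arise for both devices. Under section 6.1.1, sputum is taken because of symptoms or signs, a CAD4TB score above threshold, or the doctor's reading of the film. AeoNose plays no part, so an AeoNose-negative participant can be sputum-positive at Visit 1. A participant below the CAD4TB threshold can also give sputum, on symptoms, signs or the film reading. Section 4.2 also admits people with TB already known at entry; a miss among them is not TB confirmed during follow-up either.

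At stake is the sensitivity of AeoNose, which is part of the first primary objective, and the corresponding figure for CAD4TB. The McNemar comparison is affected too. It needs one common set of cases, but under these definitions the set depends on each test's own result.

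**Working it through.** **1. Where the participant lands.** Take an index-negative participant with a positive Visit 1 GeneXpert or culture.

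- Not a true or false positive: the index test is negative.
- Not a false negative: TB was not confirmed during follow-up, because there was none. Follow-up cannot easily be stretched to include Visit 1 sputum, since the false-positive line lists sputum results and follow-up separately.
- True negative, read literally: no TB was confirmed during follow-up, and negative sputum is not required.

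The participant escapes the true-negative cell only if that line is read as requiring actual follow-up. But section 3 ends the study after Visit 1 for participants judged healthy, so that reading would also remove most genuine true negatives.

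**2. The plan's own figure.** Section 3 expects 150-250 cases among 5000 people at 3-5%: 5000 × 0.03 = 150 and 5000 × 0.05 = 250. This reproduces. Section 4.3 plans 100-150 cases for AeoNose validation. The protocol states no expected sensitivity for this study.

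**3. Inputs for the size.**

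- S, true sensitivity. For AeoNose, 78% (low end of the Indonesian study) and 88% (Paraguayan pilot), from section 5.2. For CAD4TB, 95%, from section 1.
- f, the share of index-negative cases confirmed at Visit 1. The protocol does not give it; 0.5 to 1.0 is assumed.

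**4. Sensitivity as written.** All hits stay, and only the fraction 1 − f of misses is counted:

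literal sensitivity = S / [S + (1 − S)(1 − f)]

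Example: S = 0.78, f = 0.5 gives 0.78 / (0.78 + 0.22 × 0.5) = 0.78 / 0.89 = 87.6%.

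| True S | f = 0.5 | f = 0.7 | f = 0.9 | f = 1.0 | Overstatement, points |
|---|---|---|---|---|---|
| 78% | 87.6% | 92.2% | 97.3% | 100% | about 10-22 |
| 88% | 93.6% | 96.1% | 98.7% | 100% | about 6-12 |
| 95% | 97.4% | 98.4% | 99.5% | 100% | about 2-5 |

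Sensitivity is inflated equally whether the missed case is scored as a true negative or dropped, because it leaves the denominator either way.

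**5. Precision.** With 100 validation cases and S = 78%, the Wilson 95% interval (the method section 8.1 names for AeoNose) is 68.9-85.0%. At f = 0.9, the literal rule counts 78 hits and 22 × 0.1 = 2.2 expected misses, giving 97.3% with interval 91.0-99.2%. That interval excludes the true value.

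**6. NPV and specificity.** Illustration: 200 cases, 4800 non-cases, S = 88%, specificity 92% (the Paraguayan pilot), f = 0.9.

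- True cells: TP = 176, FN = 24, TN = 4416, FP = 384. NPV = 4416 / 4440 = 99.46%; specificity = 92.00%.
- Misses moved: 24 × 0.9 = 21.6.
- Scored as true negatives: NPV = 4437.6 / 4440 = 99.95%; specificity = 4437.6 / 4821.6 = 92.04%.
- Dropped instead: NPV = 4416 / 4418.4 = 99.95%; specificity unchanged.

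**The case against.** The strongest reply is that this is loose drafting and that nobody would apply it literally. The case definition has no time limit. Section 6.1.2 counts all cases found and how many of them each device identified. Section 8 calls the analysis cross-sectional and makes a final diagnosis after six months. Section 8.1 introduces the four outcomes as a classification of illness as present or absent, so everyone should have a place. Follow-up is not formally defined, and section 3 also uses the word for care of established cases by the national programme.

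Much of this stands: all confirmed cases were probably meant to count. That makes the correction uncontroversial, but section 8.1 holds the protocol's only definitions of the cells, and they say something else. Nor is this detail left to an analysis plan; the protocol fixes the rule.

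Three stronger readings are tempting and are not supported:

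- That the missed case falls in no cell. This holds only if the true-negative line requires actual follow-up; its words put the participant among the true negatives.
- That sensitivity will be reported at or near 100%. It reaches 100% only if every missed case is confirmed at Visit 1, and the protocol gives no figure for that share.
- That the sponsor chose a rule to discard misses. The case definition and endpoints point to a drafting slip.

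**Conclusion.** Wrong as written. The false-negative and true-negative lines in section 8.1 conflict with section 6.1.1 and move device misses confirmed on Visit 1 sputum out of the false-negative cell. The direction is certain if the text is applied: sensitivity and NPV are overstated for both devices, and specificity rises very slightly if the misses become true negatives.

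The size is conditional. For a Visit 1 share of 0.5 to 1.0, the overstatement of sensitivity is about 10-22 points at a true 78%, 6-12 at 88% and 2-5 at 95%. The effect on CAD4TB is therefore small if the 95% cited in section 1 applies. These ranges rest on the assumed share and on sensitivities borrowed from other studies. A smaller share would give a smaller bias, and there is none if analysts follow the case definition instead of section 8.1.

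**What to change.** In section 8.1, change two definitions together:

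- False negative: a negative index-test result in a confirmed TB case, whether confirmed at Visit 1 or during follow-up.
- True negative: a negative index-test result with no confirmed TB at Visit 1 or during follow-up.

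Changing only the false-negative line is not enough, because the same participant would then meet both definitions.

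Add two checks for each index test: that TP + FN equals the number of confirmed cases with a valid index-test result, and that the four cells are mutually exclusive and sum to all participants analysed. The second check will also show index-positive participants who never gave sputum, since the false-positive line asks for negative sputum results. That is a separate matter, to be settled before the sum can hold.

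The cost is two sentences and the checks. No data collection or design changes. Reported sensitivity becomes less favourable.
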